4.1.1 Visit V1: Screening visit/baseline visit/randomization General study design

Screening and the baseline visit (randomization) (Day 1) will take place in person at the participating research center. After providing informed consent for the screening process, potential participants will be asked to complete the FSS questionnaire. The questionnaire will be scored to determine whether the potential participant meets the moderate fatigue threshold. If the participant meets this threshold, as well as all other inclusion criteria and none of the exclusion criteria, they will be invited to participate in the study.

After completing the above screening activities, the research team will obtain the participant's informed consent to participate in the study. Participants who do not provide informed consent will be considered screening dropouts.

The following items will be collected at the baseline visit: participant demographics, medical history, comorbidities, risk factors, concomitant medications, physical examination findings, vital signs (including temperature, heart rate, respiratory rate, and oxygen saturation in room air), and details of the participant's COVID-19 medical history.

4.1.2 Treatment Phase (Randomization)

After all procedures for the baseline visit have been completed, all inclusion criteria have been verified, and it has been determined that the patient does not meet any exclusion criteria for the study, participants will be considered eligible for the treatment phase and then randomized to fluvoxamine, metformin, or placebo in a 1:1:1 ratio.

This randomization process will be conducted centrally or via the IWRS system, and treatment kits identified by random numbers will be allocated. The kits will be provided in a manner that prevents any individual from identifying the study drug. Participants will begin the assigned treatment (fluvoxamine, metformin, or placebo).

4.1.3 Post-treatment phase (post-study follow-up)

This phase aims to monitor the medium-term effects of using the investigational medical products, with a primary focus on the chronic fatigue scale (FSS scale) and quality of life (EQ-5D-5L scale).

4.1.4 Duration of Participation in the Study

Participation for each eligible study participant includes a screening visit (Day 1), followed by the 60-day treatment phase. A post-treatment visit will be conducted 30 days after the end of the treatment phase. The first day of medication administration is at the time of randomization and before the participant is discharged from the facility where they were enrolled in the study. The study will continue into a follow-up phase after completion of the investigational product, with follow-up visits on Day 30 and Day 60, with the final visit occurring 90 days after the randomization date (30-day post-investigational product visit). Results will be evaluated on Days 30, 60, and 90 after randomization.

A safety assessment visit will be conducted on Day 7 post-randomization to assess the tolerability of the interventions and check for possible adverse events or adverse reactions to the investigational medical product under evaluation.

Participants who discontinue the investigational product prematurely will be invited to remain in the study to complete the remaining procedures and will receive standard care for the long-term treatment and follow-up of COVID-19.

5 SELECTION AND WITHDRAWAL OF PARTICIPANTS

5.1 Number of Participants

For detailed information on the rationale for the sample size, see Section 12.

5.2 Inclusion Criteria

Participants must meet all of the following criteria to be eligible for participation in this study:

1. Age 18 years or older at the time of screening.
2. Willing and able to provide written informed consent, or have a legal representative who can provide informed consent (where approved locally and nationally).
3. A previous confirmed case of SARS-CoV-2 infection (e.g., reports having had a positive nucleic acid amplification test or a positive professional-use or self-test SARS-CoV-2 rapid antigen test).
4. Participants with clinical symptoms consistent with LONG COVID according to international definitions: (www.nice.org.uk/guidance/ng188), (https://www.who.int/publications/i/item/WHO-2019-nCoV-Post_COVID-19_condition-Clinical_case_definition-2021.1), and fatigue symptoms with an average score of at least 03 on the Fatigue Severity Scale (FSS);
5. Have a diagnosis of the most recent episode of COVID-19 within 24 months of the screening visit date.
6. Not currently hospitalized or in need of hospitalization, or having been hospitalized in an intensive care unit during the COVID-19 episode.
7. Participants with the following vital signs:
 - a. Heart rate between 55 and 100 bpm;
 - b. Temperature below 38°C;
 - c. Oxygen saturation \geq 95%.
8. Participants who are capable of becoming pregnant or whose partners are capable of becoming pregnant must agree to use appropriate contraceptive methods during the study and for up to 90 days of follow-up.
9. Symptoms of fatigue cannot be attributed to another cause (in the researcher's opinion).
10. Willingness to follow all study procedures.

5.3 Exclusion Criteria

Participants who meet any of the following criteria will not be eligible to participate in the study:

1. Known acute SARS-CoV-2 infection;
2. Inability to understand the content of the Informed Consent Form or to follow the study procedures;
3. Known prior diagnosis of myalgic encephalomyelitis/chronic fatigue syndrome, unrelated to SARS-CoV-2 infection;
4. Known pre-existing dysautonomia, unrelated to SARS-CoV-2 infection;
5. Diabetes mellitus (exclusion criterion for the Metformin and Metformin Placebo arms);
6. Known history of creatinine clearance below 30 ml/min or on dialysis;
7. Known stroke within the 3 months prior to screening;
8. Known severe anemia, defined as < 8 g/dL;
9. Body Mass Index (BMI) > 40 .
10. Known diagnosis of Lyme disease;
11. Any use of illicit drugs other than marijuana within 30 days prior to informed consent;
12. Pregnant women or women of childbearing age who do not agree to use an effective method of contraception for 90 days from the date of signing this consent form;
13. Women who are breastfeeding;
14. Expected hospitalization for elective surgical procedures lasting more than 48 hours;
15. Contraindications for the METFORMIN arm
 - a. Participants currently taking metformin;
 - b. Participants with creatinine clearance < 30 ml/min, a history of KIDIGO IV, or currently undergoing dialysis.
16. Contraindications for the FLUVOXAMINE arm
 - a. Use of serotonin reuptake inhibitors (donepezil, fluoxetine, escitalopram, paroxetine);
17. Current severe comorbid psychiatric disorder (e.g., clinical depression, anxiety, sleep disorder, eating disorder, substance abuse) that is uncontrolled and associated with significant symptoms or requiring the use of a medication contraindicated in this study;
18. Clinical history of moderate to severe hepatic impairment or hepatic cirrhosis with a Child-Pugh score of C or higher;
19. A clinical history of severe chronic lung disease with significant limitation of activities;
20. Inability of the participant to provide informed consent or adhere to the procedures proposed in the study;
21. Taking medications known to cause chronic fatigue as a side effect (except for participants with chronic cardiovascular disease who are on chronic beta-blocker therapy);
22. Known hypersensitivity and/or intolerance to fluvoxamine or metformin;

23. Any clinical condition that, in the investigator's opinion, may preclude participation in this study.

5.4 Inclusion Criteria

Participants may be randomized if they meet the inclusion criteria and do not meet any exclusion criteria for the study.

5.5 Discontinuation of the investigational product or removal of participants

5.5.1 Discontinuation of the investig

During the treatment phase of the study, the participant may discontinue the investigational product at any time and at their discretion. Similarly, the investigator may discontinue the investigational product whenever deemed necessary, whether due to an adverse event or to ensure patient safety.

Participants who discontinue treatment with the investigational drug without apparent justification after randomization and before the conclusion of the study will be encouraged to resume the medication and continue in the study as usual. If the medication is discontinued, the participant will be offered the option to remain in the study for the collection of outcomes. These participants will be treated according to the standard of care determined by the investigator.

5.5.2 Withdrawal from the Study

5.5.2.1 Withdrawal of Informed Consent

Within the provisions of informed consent and clinical judgment regarding participant safety, every effort should be made to ensure that participants complete the treatment phase and post-treatment visits. Participants will be informed that they may withdraw from the study at any time. However, if a participant withdraws from the study, every effort will be made to determine the reasons why the participant withdrew their consent. Although participants are not required to provide a reason for withdrawing consent, the investigator will make every effort to understand these reasons, fully respecting the participant's rights. The reasons for withdrawal of consent, when provided by the

participant, will be recorded in the medical record, and the center will do everything possible to ensure that the participant completes the early termination procedures described. Every effort will be made to contact a participant who fails to attend and/or does not attend a study visit by telephone to ensure that the participant is in satisfactory health.

A participant who wishes to withdraw consent for the use of investigational medical products may agree to:

- Provide information about their own health status by phone or other means until the date of the final study visit.
- Allow family physicians or family members to be contacted to provide information about the participant's health status
- Allow for a final contact at the end of the study

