3.3.2 Metformin

Participants randomized to the metformin arm will receive a dose of 500 mg twice daily for a period of 60 days. We chose to modify the metformin dose in the clinical trial for two reasons: (1) To align with the international literature, which has used a 500 mg dose every 12 hours in clinical trials to evaluate Long COVID, and (2) following a blinded analysis of the first 100 recruited participants, where we identified a dropout rate due to mild adverse effects (diarrhea, abdominal pain, nausea) in 9% of participants (common symptoms associated with the use of higher doses of metformin). In particular, the study by Bramante et al. observed a lower incidence of Long COVID in participants in the COVID OUT study's Metformin Arm, where the dose used was 500 mg every 12 hours²¹⁸. There is evidence that doses exceeding 750 mg twice daily do not result in a better inflammatory profile. The metformin dose was selected based on previous observational evidence of a dose response at

1,000 mg per day and is consistent with our previous TOGETHER study of metformin vs. placebo²¹⁹ and a similar study²²⁰. We chose to use the extended-release formulation because it causes fewer gastrointestinal side effects and has more consistent and stable bioavailability, which is an advantage in providing a uniform serum dose. Since metformin is well tolerated over long periods²²⁷, to observe its potential effect in participants with prolonged COVID-19, we chose a 60-day duration, considering the pathogenesis of the immuno-inflammatory changes present in Long COVID, which often require a therapeutic action period of 3–4 weeks for the expected effects, this being a possible explanation for the futility of using metformin in acute forms of COVID-19.

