5.5.2.2 Participant suspended by the investigator of the Study

The investigator and the designated team may use their medical judgment to terminate a participant's enrollment in the study if they determine that the participant's continued participation in the study could result in safety risks to the participant. The investigator must immediately inform the study's medical monitor of plans for the early withdrawal of a participant from the study. Participants withdrawn by the investigators will also have the opportunity to consent to the three options described above. All participants withdrawn early from the study for any reason must complete the Early Study Termination procedures described and be monitored for safety after receiving the last dose of study medication. Randomized participants who are withdrawn from the study for any reason will not be replaced.

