8.5 Procedures for early discontinuation of treatment/study withdrawal

For participants who withdraw prematurely from the study (before the Day 90 visit), the center must make every effort to ensure that the participant completes the follow-up visit, which must be conducted on the day of withdrawal or as soon as possible after withdrawal. The assessments conducted at the end-of-study visit must be the same as those for the Day 90 visit.

Participation in the study implies agreement to the proposed post-study period, which consists of two visits (conducted via telephone, social media, or telemedicine), one to be conducted on Day₉₀(30 days) and the other on Day₁₈₀(120 days) after the end of the therapeutic intervention phase.

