12.2 Randomization

Participants will be randomly assigned to one of the study arms in an equal allocation (e.g., 1:1:1). Stratified permuted block randomization will be used for this study. Randomization will be stratified by participating primary care facility with varying block sizes of participants. We will use a computer-generated interactive voice/web response system to implement randomization. For each active drug arm, there will be a placebo (or active control) arm, including for the different formulations and dosages in the study.

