12.3 Sample Size Calculation I

The sample size of 500 participants per arm and its operational characteristics were confirmed using closed-form, analytical, and numerical methods. The operational characteristics for the head-to-head comparison of the treatment arm versus the placebo arm in reducing the mean fatigue score measured by the Fatigue Severity Scale (1 to 9) on day 60 are shown in Table 2. For each pairwise comparison against the placebo arm, the Type I error rate (alpha) was set at 0.025 (one-sided) using a Bayesian normal-normal model. For the planning of our study, we assumed a plausible standard deviation value of 1.7, which was estimated from a recent study that evaluated the psychometric properties of the fatigue severity scale in participants recovering from COVID-19.¹

Table 2 : Simulated operational characteristics of our study for varying sample sizes

Dropout rate	Reduction in FSS score	Sample (n = 252)	Sample (n = 500)	Sample (n = 752)	Sample (n = 1000)
0.0	0.00	2.5%	2.5%	2.5%	2.5%
	0.15	13.2%	22.6%	32.3%	41.5%
	0.30	41.8%	71.2%	87.8%	95.2%

Dropout rate	Reduction in FSS score	Sample (n = 252)	Sample (n = 500)	Sample (n = 752)	Sample (n = 1000)
	0.45	76.8%	97.1%	99.7%	100.0%
2.5	0.00	2.5%	2.5%	2.5%	2.5%
	0.15	12.9%	22.0%	31.5%	40.5%
	0.30	40.6%	69.7%	86.8%	94.7%
	0.45	75.4%	96.6%	99.7%	100.0%
5.0	0.00	2.5%	2.5%	2.5%	2.5%
	0.15	12.6%	21.6%	30.8%	39.6%
	0.30	39.5%	68.5%	85.9%	94.1%
	0.45	73.9%	96.3%	99.6%	100.0%
10.0	0.00	2.5%	2.5%	2.5%	2.5%
	0.15	12.2%	20.6%	29.4%	37.8%
	0.30	37.7%	66.1%	84.0%	92.9%
	0.45	71.5%	95.4%	99.4%	99.9%

Thus, the clinical trial will recruit 1,500 participants, divided into three groups of 500 participants each. With the proposed sample size of 500 participants in each group, the study will have adequate statistical power to detect a clinically significant treatment effect. A difference of 0.45 has been suggested as the minimum clinically important difference (MID) on the fatigue severity scale in population groups of participants with multiple sclerosis and chronic fatigue.² Even with a 10% dropout rate, our estimated power to detect a difference of 0.45 is above 90%.

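### Sections 5.5.2.1 and 5.5.2.2 conflict with 4.1.4 and 5.5.1 and do not provide for the day-60 FSS, so an obtainable primary outcome can go missing in participants handled there

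*Protocol*

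**What the plan says.** Two sections keep a participant who stops the drug in the study.

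- Section 4.1.4: "Participants who discontinue the investigational product prematurely will be invited to remain in the study to complete the remaining procedures".
- Section 5.5.1, which covers stops by the participant and stops by the investigator for an adverse event or for safety: "If the medication is discontinued, the participant will be offered the option to remain in the study for the collection of outcomes".

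Two sections under the heading of withdrawal from the study say something else.

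- Section 5.5.2.1: "A participant who wishes to withdraw consent for the use of investigational medical products may agree to" three things. These are reporting on their health by telephone or otherwise up to the last visit, letting a family doctor or relatives be contacted, and one contact at the end of the study.
- Section 5.5.2.2, on ending a participant's enrolment for safety: "Participants withdrawn by the investigators will also have the opportunity to consent to the three options described above". It also requires the early-termination procedures.

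Section 8.5, whose heading joins treatment discontinuation with study withdrawal, places the early-termination visit on the day of withdrawal or as soon as possible afterwards: "The assessments conducted at the end-of-study visit must be the same as those for the Day 90 visit". Table 1 marks the FSS in that column. The glossary defines premature withdrawal as a point after which no assessments are planned, except follow-up for progression or survival. It defines stopping treatment separately, as something that may or may not coincide with withdrawal.

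**The concern.** A participant who withdraws consent to the drug alone has stopped the drug and has not refused follow-up. Sections 4.1.4 and 5.5.1 keep that person in the study for outcomes. Section 5.5.2.1 treats the same person as a study withdrawal, with options that name no questionnaire. A site has no stated rule for which section governs.

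The primary comparison is the FSS at day 60 (Protocol Overview, 2.1, 12.11) under intention to treat (12.4). If participants who leave because of drug effects are handled under 5.5.2, their day-60 FSS may be missing in relation to treatment, and an analysis of the remaining scores can be biased. The loss would be avoidable, because the Overview and section 8.3 already allow visits by telephone, and the Overview says so for day 60 expressly.

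**Working it through.** **1. The routes side by side**

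| Situation | Section | Stated route to a day-60 FSS |
|---|---|---|
| Drug stopped by participant or investigator | 5.5.1, 4.1.4 | Yes: may stay for outcomes and remaining procedures |
| Consent withdrawn for the drug only | 5.5.2.1 | None named; three options |
| Removed from the study by the investigator for safety | 5.5.2.2 | None named; same three options plus early termination |
| Early-termination visit | 8.5, Table 1 | FSS on or near the day of withdrawal |

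The fourth row does not fill the gap. The FSS asks about the past week (9.4), and the day-60 window is ±7 days in Table 1 or ±5 days in 8.3. A participant who leaves at day 20 has a day-20 FSS and no planned day-60 FSS.

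**2. Power**

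Inputs from section 12.3: 500 per arm, SD 1.7, one-sided alpha 0.025, difference 0.45, 10% dropout. Table 2 states 95.4%.

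- Fixed design: power = Φ(0.45 / (1.7 × √(2/450)) − 1.96) = Φ(3.97 − 1.96) = 97.8%. This is higher than the stated figure.
- Four equally spaced looks with a constant Pocock-type bound (z = 2.361, simulated): 95.7%, against 95.4% stated. All 21 cells of Table 2 that were checked agree within 2 points. The bound is inferred, because the protocol gives no thresholds.

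With that design, and day-60 scores missing in both arms for reasons unrelated to outcome, power for 0.45 is:

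| Missing | 9% | 10% | 13.5% | 20% |
|---|---|---|---|---|
| Power | 95.9% | 95.7% | 95.0% | 93.3% |

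Power is not the problem.

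**3. Bias**

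Let m be the share of an active arm without a day-60 FSS, with none lost on placebo. Let g be how much worse the lost participants score than those retained. The true active mean is the retained mean plus m × g. The complete-case difference therefore favours the drug by m × g. Both m and g are assumptions; the protocol gives neither.

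The one-sided type I error for a single look is 1 − Φ(1.96 − m × g / SE), with SE = 1.7 × √(1/500 + 1/(500 × (1 − m))).

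| m | g | Bias m × g | Share of 0.45 | Type I error (nominal 2.5%) |
|---|---|---|---|---|
| 3% | 0.5 | 0.015 | 3% | 3.4% |
| 5% | 1.0 | 0.05 | 11% | 6.7% |
| 9% | 1.0 | 0.09 | 20% | 12.7% |

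If the same share is lost in both arms with the same score gap, the bias is m × g − m × g = 0.

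**The case against.** The strongest reply is that the protocol already separates stopping the drug from leaving the study. Section 5.5.1 covers investigator stops for adverse events and keeps those participants in for outcomes. Section 5.5.2.1 asks for every effort to complete post-treatment visits. Its options are permissive, and reporting on health by telephone up to the last visit spans day 60 and could carry the FSS. Section 5.5.2.2 is a different decision, made when remaining in the study is itself judged a risk. Multiple imputation (12.4) and a missing-data analysis (12.6) are planned, and day-30 and early-termination scores could inform them.

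Most of this stands, and it limits the point to participants handled under 5.5.2. It does not remove the contradiction: drug-only withdrawal of consent is still filed as study withdrawal, and the FSS is nowhere named there.

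A reader might infer that day 60 is lost in everyone who stops for drug effects, and might size this from section 3.3.2: "we identified a dropout rate due to mild adverse effects (diarrhea, abdominal pain, nausea) in 9% of participants". Placing all nine of the first 100 on metformin (9 of about 33, or 27%) with a gap of 1.0 point would give 0.27, which is 60% of 0.45. The documents do not support that reading. The 9% comes from a blinded analysis, is pooled over arms and precedes the metformin dose change. The text does not say that these participants lack a day-60 FSS. The one-sided split and the score gap would also be pure assumption.

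**Conclusion.** The conflict is real and narrow. Followed as written, 5.5.2.1 and 5.5.2.2 can leave the day-60 primary outcome uncollected in participants who would have given it by telephone. How many is unknown, and ordinary drug stops under 5.5.1 are not affected.

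If 3% to 9% are lost on active drug only, and those lost score 0.5 to 1.0 point worse, a complete-case analysis is biased by about 0.015 to 0.09 FSS points in favour of the drug. The bias is zero if loss is balanced, and imputation may reduce it. Power for 0.45 stays above 90% even with 20% missing.

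The reason to act is that scores missed in this way cannot be recovered later, while section 12.8 expects data from every participant.

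**What to change.** Reconcile sections 4.1.4, 5.5.1, 5.5.2.1, 5.5.2.2 and 8.5 so that stopping the drug is kept apart from leaving the study.

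- In 5.5.2.1 and 5.5.2.2, make the first option offered the FSS and EQ-5D-5L at the scheduled days 30, 60 and 90 by telephone, for anyone who agrees. Keep the three existing options for those who decline.
- In 8.5, record any withdrawal-day FSS under its actual date, in addition to the scheduled day-60 FSS and not in its place.
- Leave the investigator's discretion to end participation for safety unchanged. The change concerns outcome collection only.

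The cost is protocol and consent-form wording and a few extra calls in a mode already allowed. More off-treatment scores will enter the primary analysis, which is what intention to treat implies.
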